8.2.2 Sample scheduling and missing samples

- Weekly blood samples collected during RT/CRT for HPV+ patients should be collected on the same day each week where possible.
- Where HPV+ patients have their radiotherapy treatment extended into week 7 it is requested that an additional blood sample is collected at the end of RT/CRT treatment.
- For HPV- patients only if the baseline sample is not collected prior to RT/CRT treatment, the patient should be withdrawn from the INOVATE study.
- For HPV+ patients only if the baseline sample is not collected prior to RT/CRT treatment and both the RT week 1 and RT week 2 samples are missing, the patient should be withdrawn from the INOVATE study.
- Patients who miss sample collection at any of the time-points (other than missing all three of: baseline, RT week 1 and RT week 2) will continue in the study and will be included in final analysis.
- As the 12 week post-RT/CRT blood sample informs the primary endpoint it may be collected anytime between 11 18 weeks post-RT/CRT.
- If a patient is found to have residual disease, recurrence or progression the blood samples should still be collected according to the time lines specified in the protocol.
- If the patient does not complete RT for any reason, they should be withdrawn and sample collection will cease.

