4. STUDY DESIGN

This is a multicentre, prospective biological research study involving the collection of tissue (blood and tumour) and routine clinical data. Any reference to "treatment" in this protocol refers to RT/CRT treatment delivered as per standard of care, and does not constitute an intervention defined by the study protocol. The only intervention of this study protocol is the collection of tissue and blood samples.

Samples will be collected from newly diagnosed patients with T1-T2/N1-3 or T3-T4/N0-3 carcinoma of the oropharynx, with known tumour HPV status and due to receive radical RT/CRT. Patients who are suitable for RT/CRT will be registered in the study after diagnosis (defined as confirmed histological diagnosis, and staging) and before administration of RT/CRT. Initially the study will be open to both HPV+ and HPV- patients (negative controls), but following the recruitment of 48 HPV- patients sites will be notified that no further HPV – patients should be approached about the study. The frequency and timing of donated blood and tissue samples will depend on whether the patient is HPV+ or HPV- and is summarized in the study schema and in Table 1.

4.2 Clinical Follow up.

Sites will be required to provide clinical data from routine follow-up. Assessment of local control at 3 months following the completion of RT/CRT will be assessed using ¹⁸F-FDG PET-CT.

Data will be collected from ¹⁸F-FDG PET-CT scans performed as part of routine practice. Sites are requested to send a copy of the report for the 3 month ¹⁸F-FDG PET-CT scan to the ICR-CTSU office. This report should be redacted to protect the patient's personal data.

Please note that ICR-CTSU may request redacted reports of other ¹⁸F-FDG PET-CT scans carried out during the lifetime of the study.

For further details regarding the submission of these reports please see the INOVATE study guidelines.

Data on the status of disease recurrence will be requested from routine clinical assessment at 3, 6, 9 and 12 months post-RT/CRT. It is anticipated that further radiological review will be carried out as per standard practice if clinical assessment raises the suspicion of recurrent disease. It is anticipated that patients with confirmed residual disease, disease recurrence or progression will be recommended to have a biopsy and/or neck dissection (See Section 9).

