8.2 Blood Sample Collection

All blood samples will comprise one 20 mL blood sample collected in 2 x 10 mL Streck[™] tubes. As the blood samples are collected in Streck[™] tubes they should NOT be stored in the refrigerator at any time. For further details on the use of Streck[™] tubes please refer to the INOVATE Sample Collection Guidelines.

The majority of blood samples will be taken at the same time as routine blood collection. However all patients will be required to donate a number of samples after the 6 week time point which may be in addition to standard practice (depending on local practice at the recruiting centre).

8.2.1 Additional blood Samples for HPV+ patients pre and post surgery.

HPV+ patients only: an additional 20 mL blood sample (2 x 10 mL Streck[™] tubes) for HPV DNA analysis will be collected before and after any surgical procedures or biopsies performed post-RT/CRT. Samples may be collected at any time between confirmation of residual disease/recurrence and surgery and before hospital discharge after surgery.

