8.4 Clinical Data Collection

Electronic (e) Case Report Forms (CRFs) will be used for the collection of study data. Clinical data will be stored and analysed at ICR-CTSU who will provide guidance to sites to aid the completion of the eCRFs.

The following data will be collected on electronic case report forms:

At baseline: age, sex, smoking history, detailed tumour staging, HPV (p16Ink4A) status.

Post RT/CRT treatment: radiotherapy start date and schedule.

At 12 week post RT/CRT: results of 12 week ¹⁸F FDG PET-CT scan (and any repeated scans), carried out as per local practice for assessment of local control. If an HPV+ patient is found to have residual disease at the 12 week assessment and is scheduled to receive surgery/biopsy this should be reported to the ICR-CTSU trials office in an expedited fashion on the appropriate eCRF as soon as the surgery/requirement for biopsy is is confirmed.

During follow up: Information on the status of disease recurrence will be collected at 3, 6, 9 and 12 months post-RT/CRT. It is anticipated that further radiological review will be carried out as per standard practice if clinical assessment raises the suspicion of recurrent disease.

9. PROCEDURE FOLLOWING CONFIRMATION OF RESIDUAL DISEASE (AT 12 WEEKS), DISEASE PROGRESSION OR RECURRENCE

If the confirmation of residual disease following the 12 week ¹⁸F FDG PET-CT scan or later confirmation of disease progression/recurrence will require the patient to undergo surgery/biopsies this should be reported to the ICR-CTSU trials office in an expedited manner on the appropriate eCRF.

It is anticipated that patients with residual disease, disease progression or recurrence who meet the following criteria following radiological assessment will undergo neck surgery:

a) positive PET-CT and/orb) equivocal PET-CT with lymph node > 1cm.

If the 12 week ¹⁸F FDG PET-CT scan is repeated following equivocal results, details of the repeat scan should be notified to ICR-CTSU on the appropriate eCRF.

It is anticipated that patients who have residual disease at primary site will undergo a biopsy of this site. However if the 12 week ¹⁸F FDG PET-CT scan is repeated (according to local practice) following equivocal results, details of the repeat scan should be notified to ICR-CTSU on the appropriate eCRF.

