12.2 Endpoint Definitions

12.2.1 Primary endpoint

The specificity of HPV-detect (using plasma HPV DNA levels) in correctly identifying those with no residual disease, at 3 months following completion of primary RT/CRT is defined as the proportion patients who are HPV-detect negative among those with no residual disease according to 18F-FDG PET-CT at the same time point.

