12.3 Statistical Analysis Plan

Analysis of the primary endpoint will include all patients in the HPV+ oropharyngeal cancer cohort who are evaluable i.e. have both HPV-detect (plasma DNA) and ¹⁸F-FDG PET-CT results at 3 months following completion of primary RT/CRT. Specificity will be calculated and presented with associated exact 95% confidence interval. Primary analysis will be performed when the last patient registered has reached the 3-month time point. Sensitivity will be analysed similarly.

Based on the high negative predictive value of HPV detect (>90%), a small proportion of patients with residual disease as per ¹⁸F-FDG PET-CT will potentially have a negative HPV-detect. We will report these as a proportion with associated exact 95% confidence intervals.

We will not alter the clinical management of these patients, but aim to collect samples for all patients up to one year, to track HPV DNA in these patients and correlate this to disease outcome.

Secondary endpoints of sensitivity, and the proportion of patients with no residual disease on biopsy/neck dissection amongst those with residual disease according to 18F FDG PET-CT but HPV-detect negative at 3 months following completion of primary chemo-radiation will be analysed using the same patient population and as per the primary endpoint. The proportions will be presented with associated exact 95% confidence interval

Association between plasma HPV DNA levels at different timepoints and clinical and radiological response up to a period of 12 months post-RT/CRT will be investigated using logistic regression models.

Analysis of sensitivity and specificity of HPV-detect in measuring HPV DNA levels at baseline will be calculated and presented with associated exact 95% confidence interval from all patients with paired data from diagnostic tissue and HPV-detect at baseline and will include both HPV+ and HPV- (negative control) patients.

Analysis of the molecular features/characteristics of the tumour tissues and to determine changes/conservation of these features in paired plasma samples.

Kinetics of change in plasma HPV DNA levels during and immediately following RT/CRT will be displayed graphically, separately for HPV+ and HPV- patients.

Full details of analyses of all primary and secondary endpoints will be described in the Statistical Analysis Plan in accordance with ICR-CTSU Standard Operating Procedures.

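### The 3-month HPV-detect sample may be drawn after PET-driven neck surgery, which can bias sensitivity and the histology-negative proportion downward, though not primary specificity

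*Protocol*

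**What the plan says.** - **Sample window.** Protocol 8.2.2: "As the 12 week post-RT/CRT blood sample informs the primary endpoint it may be collected anytime between" 11 and 18 weeks. The same list says that patients found to have residual disease, recurrence or progression keep to the protocol's sampling times.
- **Endpoint.** Protocol 12.2.1 defines specificity as the share of HPV-detect negatives "among those with no residual disease according to 18F-FDG PET-CT at the same time point". Section 12.2.2 ties sensitivity to the same time point, among PET-positive patients.
- **Scan.** Section 4.2: "Assessment of local control at 3 months following the completion of RT/CRT will be assessed using" PET-CT, taken from routine practice. Section 8.4 also collects the scan result ("and any repeated scans), carried out as per local practice for assessment of local control"). No maximum interval between scan and blood draw is set.
- **Surgery.** Section 9 anticipates neck surgery after a positive PET-CT, or after an equivocal one with a node over 1 cm, and a biopsy for residual disease at the primary site. It gives no time from scan to procedure.
- **Peri-procedure blood.** Section 8.2.1 adds samples before and after any post-RT/CRT procedure in HPV+ patients: "Samples may be collected at any time between confirmation of residual disease/recurrence and surgery", and again before hospital discharge. They are described as additional and are not linked to the 3-month value.
- **Analysis.** Section 12.3 calls a patient evaluable when both results exist at 3 months. It adds: "Primary analysis will be performed when the last patient registered has reached the 3-month time point". The secondary proportions use the same population and are analysed in the same way as the primary endpoint.

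**The concern.** The PET-CT describes the patient before any salvage surgery. Under 8.2.2 the blood sample compared with it may be taken up to 18 weeks after treatment, and section 9 sends PET-positive patients to surgery after the scan. If the node is removed first and plasma HPV DNA clears, the record reads PET-positive, histology-positive, HPV-detect negative. That looks like a cancer missed by the assay, when the sample was in fact taken after the cancer had been removed.

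The two results affected are sensitivity and the proportion without disease on histology among PET-positive/HPV-detect-negative patients. The second bears directly on the purpose stated in section 2, which is to avoid unnecessary neck dissections and biopsies.

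**Working it through.** **1. The plan's own figure.** Inputs from 12.1: null specificity 0.85, true specificity 0.95, two-sided alpha 0.05, power 80%, PET-positive prevalence 25%, loss 30%.
- Exact binomial test with upper tail 0.025: the smallest n with at least 80% power is 75 PET-negative patients. The test passes at 70 or more HPV-detect negatives (tail probability 0.0234, power 0.828).
- 75 / 0.75 = 100 evaluable, and 100 / 0.70 = 142.9, so 143 registered. Both figures reproduce.
- PET-positive patients expected: 100 × 0.25 = 25.

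**2. Can a post-excision sample qualify?** Scan at 12 weeks, window to 18 weeks: 18 − 12 = 6 weeks in which surgery may come before the scheduled draw. Evaluability in 12.3 carries no before-procedure condition. If surgery falls inside the window, the scheduled, pre-procedure and post-procedure samples can all lie within it, and the protocol does not say which supplies the 3-month value.

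**3. Which endpoints are exposed?**
- Specificity has only PET-negative patients in its denominator. Section 9 routes positive scans, and equivocal scans with a node over 1 cm, to neck surgery. Specificity is therefore reached only if such equivocal scans are counted as negative.
- Sensitivity has the PET-positive patients as its denominator, so it is exposed.
- The histology proportion is computed among PET-positive/HPV-detect-negative patients, so it is exposed.

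**4. Size.** Let k be the number of PET-positive patients whose HPV DNA was detectable before surgery and has cleared by a post-excision draw.
- Loss in sensitivity = k / 25, which is 4 points per patient.
- Let N be the histology-negative and M the genuinely missed histology-positive patients in the discordant group. The proportion falls from N / (N + M) to N / (N + M + k) when the k patients have disease on histology.

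Illustration, on assumed figures: 25 PET-positive, 8 with true disease, an otherwise perfect assay (N = 17, M = 0).

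| k | Sensitivity against PET-CT | Histology-negative proportion |
|---|---|---|
| 0 | 8/25 = 32% | 17/17 = 100% |
| 1 | 7/25 = 28% | 17/18 = 94% |
| 2 | 6/25 = 24% | 17/19 = 89% |
| 4 | 4/25 = 16% | 17/21 = 81% |

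The exact 95% interval for the proportion moves from 80–100% at k = 0 to 58–95% at k = 4. The documents give no basis for choosing k, and zero is possible.

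**5. Data cut.** Taking 3 months as about 13 weeks, the trigger in 12.3 could fall 18 − 13 = 5 weeks before the last permitted sample.

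**The case against.** - **The primary endpoint is safe.** This stands. A reader might infer from the wording of 8.2.2 that the trial's main result is compromised. The documents do not support that: PET-negative patients are not on the surgical route. HPV DNA could also drift in PET-negative patients during the window, but the protocol gives no rate of change, so no effect on specificity can be claimed from it.
- **The same time point is a visit label, and visits have windows.** This stands in part. A window alone is no contradiction. The difficulty is that this one can span an operation that removes what is being measured.
- **The pre-procedure sample already exists, and choosing among samples belongs in the SAP.** The sample does exist, which makes the fix cheap. But the protocol itself fixes the window, keeps it open for patients with residual disease, and defines evaluability without a before-surgery condition. Followed as written, it admits the wrong sample. A SAP that is not shown may restrict the analysis further.
- **The size is unproven.** This stands. In the pilot (section 2), none of 7 PET-positive patients had viable tumour and all were HPV-detect negative, so k would have been zero. Seven patients exclude little, however: the exact 95% upper limit for viable tumour is 1 − 0.025^(1/7) = 41%.
- **A biopsy does not remove the disease.** This stands. The argument concerns excision, not diagnostic biopsy of the primary site.
- **The error runs against the assay.** Also true: it would not falsely support sparing surgery. It could still make a good test appear to miss cancers.
- **The 3-month trigger can be read to include its window, and specificity needs no histology.** Both are fair, so the data cut is a minor matter. The histology-based proportion nevertheless depends on results that arrive later.

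**Conclusion.** The point holds for two secondary endpoints. As written, a sample taken after excision can serve as the 3-month HPV-detect value and be paired with a scan from before surgery. Sensitivity then falls by 4 points for each PET-positive patient who was detectable before surgery and cleared by the draw, and the histology-negative proportion falls when such a patient has disease on histology.

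The 4-point figure assumes 25 PET-positive patients among 100 evaluable. The number affected cannot be derived, since no PET-to-surgery interval is stated, so a particular total bias should not be quoted as expected. Primary specificity is unaffected by this mechanism, unless equivocal scans that led to surgery are classed as showing no residual disease. The timing of the data cut is a clarification, not a separate error.

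**What to change.** In 8.2.2 and 12.3, state that:

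1. The analysed 3-month HPV-detect value must come from a sample taken before any post-RT/CRT surgical excision. Applied to every HPV+ patient, including those with equivocal scans, this also closes the one route to the primary endpoint.
2. If the scheduled sample falls after excision, the pre-procedure sample already collected under 8.2.1 is used. If there is none, the patient is not evaluable for the 3-month comparison.
3. Where several samples qualify, the one nearest the PET-CT date is used.
4. The analysis data cut follows closure of the last patient's 18-week window, and the histology-based secondary endpoint is analysed once histology is available.

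The cost is small: a few patients may become non-evaluable and the data cut moves by a few weeks. No extra blood is taken, and clinical management is unchanged.

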8.3 Storage, labelling and postage of blood and tissue samples

All INOVATE blood samples and tissue samples should be collected, labelled, stored and shipped as detailed in the INOVATE Sample Collection Guidelines.

All samples must be labelled with the patient's study identifier (patient Registration Number), date of birth and date of sample to enable cross-referencing.

All samples should be posted to the central laboratory at the Institute of Cancer Research in the packaging provided.

Tissue Blocks

Archival blocks will be collected in batches. ICR-CTSU will notify the sites when block collection is required. All samples should be sent by post to the following address:

Room 35 CBO, Chester Betty Laboratories Targeted Therapy Team Cancer Biology The Institute of Cancer Research [name]

Research Blood Samples

All research blood samples should be sent by post within 48-72 hours to the following address:

Room 35

CBO, Chester Betty Laboratories Targeted Therapy Team Cancer Biology The Institute of Cancer Research [name]

Samples labelled in an anonymised manner may be shared with external institutions, including those outside the UK and EU, for future research.

8.4 Clinical Data Collection

Electronic (e) Case Report Forms (CRFs) will be used for the collection of study data. Clinical data will be stored and analysed at ICR-CTSU who will provide guidance to sites to aid the completion of the eCRFs.

The following data will be collected on electronic case report forms:

At baseline: age, sex, smoking history, detailed tumour staging, HPV (p16Ink4A) status.

Post RT/CRT treatment: radiotherapy start date and schedule.

At 12 week post RT/CRT: results of 12 week ¹⁸F FDG PET-CT scan (and any repeated scans), carried out as per local practice for assessment of local control. If an HPV+ patient is found to have residual disease at the 12 week assessment and is scheduled to receive surgery/biopsy this should be reported to the ICR-CTSU trials office in an expedited fashion on the appropriate eCRF as soon as the surgery/requirement for biopsy is is confirmed.

During follow up: Information on the status of disease recurrence will be collected at 3, 6, 9 and 12 months post-RT/CRT. It is anticipated that further radiological review will be carried out as per standard practice if clinical assessment raises the suspicion of recurrent disease.

9. PROCEDURE FOLLOWING CONFIRMATION OF RESIDUAL DISEASE (AT 12 WEEKS), DISEASE PROGRESSION OR RECURRENCE

If the confirmation of residual disease following the 12 week ¹⁸F FDG PET-CT scan or later confirmation of disease progression/recurrence will require the patient to undergo surgery/biopsies this should be reported to the ICR-CTSU trials office in an expedited manner on the appropriate eCRF.

It is anticipated that patients with residual disease, disease progression or recurrence who meet the following criteria following radiological assessment will undergo neck surgery:

a) positive PET-CT and/orb) equivocal PET-CT with lymph node > 1cm.

If the 12 week ¹⁸F FDG PET-CT scan is repeated following equivocal results, details of the repeat scan should be notified to ICR-CTSU on the appropriate eCRF.

It is anticipated that patients who have residual disease at primary site will undergo a biopsy of this site. However if the 12 week ¹⁸F FDG PET-CT scan is repeated (according to local practice) following equivocal results, details of the repeat scan should be notified to ICR-CTSU on the appropriate eCRF.

Prior to opening, centres will be required to confirm that they fulfil minimal surgical quality assurances stipulated by the INOVATE surgical co-investigators and that they will adhere to the surgical recommendations in Section 9.1.

Data will be requested from routine follow-up visits relating to surgical outcome and disease status.

9.1 Surgical recommendations for INOVATE patients requiring neck surgery (as per national guidelines).

• The surgeon performing the procedure will work within a recognised MDT within a cancer network in the UK.

It is recognised that the extent of neck dissection varies across geographical regions, with an increasing trend for less extensive neck dissections. In addition, the number of nodes in a radiated neck will be low, and will not serve as a quality indicator as it does in the previously untreated neck. Thus the criteria for this study will take two forms:

A. Neck dissection levels

- 1. Based on surgeon preference and the size and site(s) of abnormality as seen on the PET-CT/CT scan, current practice varies from a nidusectomy alone to multilevel dissection. Hence, from a pragmatic perspective, the following procedures are recommended:
 - a. In instances where a solitary focus is the abnormality on PET-CT, the procedure should include at a minimum the abnormal nidus (lymph node).
 - b. In the presence of multiple foci, but at the same neck level, a minimum of two adjacent levels in addition to the abnormal node being targeted is recommended (see Table 2).

Table 2: Study specific neck dissection recommendations

| Abnormal node level | Levels to be removed by neck dissection |
|---------------------|---|
| lla | llb and lll |
| 111 | II and IV |
| IV | III and Vb |
| 1 | II and III |

c. In the event of multiple abnormal nodes at several levels, a 5 level dissection is recommended.

2. The abnormal nodes should be clearly identified and orientated in the specimen sent to the lab.

B. Correlation of the dissected specimen with the radiological findings

The neck treated by radiation can be affected by fibrosis making for a challenging procedure. To ensure that the abnormal nodes have been removed by the surgical procedure, the INOVATE study team will randomly choose 20% of neck dissections and correlate the sizes of the nodes identified in the histology report with the radiological findings. Allowing for a 30% shrinkage with specimen fixation, the maximum dimension of the nodes identified as being abnormal in the specimen should correlate with the maximum dimension on radiologic imaging.

Any further clinical treatment is at the discretion of the treating clinician and should follow standard of care.

